5.1 Sample Size Determination

Based on an 80% power analysis, incidence rates reported from past studies, and a ratio of 1:1:1 cohort size between the different treatment groups involved, a total of 200 patients will be included in the study. Given an estimated 700 total hip and knee replacements done in a quarter each year at NYULMC, the project is scheduled to take a total of 7 months. It is estimated that 50% of all patients will be approached to be consented

from these 700 patients (a total of 350 patients will be enrolled to reach the target number of participants), and an estimated 60% of these patients will agree to follow through with the study.

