Wound closure techniques have been well-studied in a variety of surgical specialties, however, the level of evidence reported in the literature in regards to TJA is scarce. Thus, the current randomized, control trial study aims to investigate the perioperative outcomes and costs of various wound closure techniques including zipper technology, monocryl suture plus Dermabond, and polyester plus Dermabond wound closure techniques. The zipper wound technology is a new wound closure device that is an alternative to the commonly used conventional staples and sutures. The device acts like a scaffold to stabilize the adjacent sides of a wound in order to minimize forces that can disrupt normal healing of the skin. Monocryl suture plus Dermabond is a commonly used combination of wound closure techniques today. Finally, the polyester plus Dermabond closure techniques combines the OCA topical skin adhesive with a flexible, self-adhesive polyester mesh that has proven to reduce wound closure times and have a significant greater skin holding strength than skin staples or subcuticular sutures in one study. Although there have been prior studies measuring the efficacy of these closure techniques individually, none have compared these three particular ones following TJA. Furthermore, in order to provide the highest level of evidence as possible for the study, it will be conducted in a randomized fashion.

CONFIDENTIAL

This material is the property of the NYU School of Medicine and Langone Medical Center. Do not disclose or use except as authorized in writing by the study sponsor

The hypothesis of the study is that there will be reduced complications rates, improved outcomes, and overall cost reduction for the zipper technology versus the other two closure techniques.

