1.3 Clinical Data to Date

A recent meta-analysis[22] compared this surgical zipper technique to conventional sutures in closing surgical wounds based on 4 randomized, control trials. The study showed that there was a similar incidence of postoperative complications, less time for incision closure, less cost for personnel involved in the procedure as well as total operating times, and higher levels of patient comfort for the zipper technique cohort.

Research Risks and Benefits

Risks

There are low associated risks with all three closure techniques. Commonly documented complications associated with all closure techniques include infection, abscess formation, hematoma formation, dehiscence, prolonged discharge, and allergic reactions. These risks are minimal overall with minimal risk differences between each technique. Thus, at worst, there will be minimal change in risks whether patients are randomized or have the option to choose a specific technique.

Benefits

There may be no direct benefit from agreeing to participate in this study. It is hoped that the knowledge gained will be of benefit to others in the future.

1.4 Primary and secondary objectives:

Primary objective: to identify the rate of complications associated with each type of wound closure technique. Some of these complications will include infection, abscess formation, dehiscence, prolonged drainage, allergic reactions, among others.

Secondary objective: to determine the cost effectiveness of each of these wound closure techniques, which will be calculated by the differences in supply costs, total lengths of operation, and postoperative complications.

CONFIDENTIAL

This material is the property of the NYU School of Medicine and Langone Medical Center. Do not disclose or use except as authorized in writing by the study sponsor

2 Study Design

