2.2 Primary Study Endpoints

Each complication will be documented for every patient. The rates of complication will be analyzed individually for each technique, and risk ratios will be conducted between techniques to determine which technique has the lowest risk of developing a complication. Complications include infection, abscess formation, dehiscence, prolonged drainage, allergic reactions, among others.

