3.2 Method for Assigning Subjects to Treatment Groups

Names of patients who are consented for the study will be inputted into a computer and randomized to one of the three treatment groups based on an alternating method. A randomized control trial will provide the highest level of evidence without altering the potential risks to the patient as all three wound closure techniques have been found to have comparable complication rates.

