5.2 Statistical Methods

Data on patient baseline characteristics, procedural characteristics, perioperative outcomes, functional outcomes, and costs will be collected. Single variable and multivariate statistical analysis will be performed to assess the aforementioned data points. Dichotomous data outcomes will be analyzed using odd ratios and chi-squared tests while continuous data points will be analyzed using Student t-tests. Each complication will be documented for every patient. The rates of complication will be analyzed individually for each technique, and risk ratios will be conducted between techniques to determine which technique has the lowest risk of developing a complication. Complications include infection, abscess formation, dehiscence, prolonged drainage, allergic reactions, among others. Cost effectiveness will be determined by the differences in quality metrics such as LOS, readmissions, cost of supplies, and differences in wound closure time between the different wound closure techniques. Each of these variables will be calculated based on the associated hospital costs and analyzed to determine the most cost effective wound closure technique.

CONFIDENTIAL

This material is the property of the NYU School of Medicine and Langone Medical Center. Do not disclose or use except as authorized in writing by the study sponsor

6 Safety and Adverse Events

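### Section 5.1's unqualified 80% power for 200 patients cannot be checked and does not fit the protocol's own account of low, minimally different complication rates

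*Combined protocol and SAP*

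**What the plan says.** Section 5.1 (Sample Size Determination) is the only place where the sample size is justified: "Based on an 80% power analysis, incidence rates reported from past studies, and a ratio of 1:1:1 cohort size between the different treatment groups", leading to 200 patients in total. No complication rate, target difference, alpha, sidedness or contrast is given there or anywhere else in the document.

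The comparison that this power should serve is the primary endpoint. Section 2.2 says that "risk ratios will be conducted between techniques to determine which technique has the lowest risk of developing a complication". Section 5.2 names the test: "Dichotomous data outcomes will be analyzed using odd ratios and chi-squared tests". The hypothesis at the end of section 1.1 is directional: "there will be reduced complications rates, improved outcomes, and overall cost reduction for the zipper technology versus the other two closure techniques".

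The protocol characterises existing evidence in three places, always in words:

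- Risks, under section 1.3: "There are low associated risks with all three closure techniques", and then "These risks are minimal overall with minimal risk differences between each technique".
- Section 1.3 also cites a meta-analysis of four randomised trials of zipper versus sutures and reports a similar incidence of complications.
- Section 3.2: "all three wound closure techniques have been found to have comparable complication rates".

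**The concern.** Missing inputs alone would be a reporting gap. Here there is more. Section 5.1 says that its inputs are past incidence rates, and the protocol's own summary of past evidence is that rates are low and hardly differ. A reduction cannot exceed the comparator rate, so from a low rate a trial of this size reaches 80% power only if complications are almost eliminated.

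The IRB and later readers will take 80% as the chance of detecting a real difference on the primary endpoint. If the true gap is a few points, a non-significant result is the likely outcome and could be misread as evidence that the three closures perform alike.

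**Working it through.** **Reproducing the plan's figure.** This cannot be done, because no rates, alpha or contrast are stated. The calculation is therefore inverted: which differences give 80% power at the stated size?

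**Inputs.** From section 5.1: 200 patients at 1:1:1, so 200/3 = 66.7 per arm (67 is used below), and 80% power. From section 5.2: the chi-squared test. Assumed, because not stated: two-sided alpha 0.05, one pairwise comparison, no continuity correction, no multiplicity adjustment and no dropout.

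**Best-case floor.** Suppose that one arm has a true rate of zero. With k events against 0 of 67, the Pearson statistic is 134k/(134 − k), and the critical value is 3.84.

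- k = 3: 402/131 = 3.07, not significant.
- k = 4: 536/130 = 4.12, significant.

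So at least 4 events are needed in the other arm. P(X ≥ 4) for X ~ Binomial(67, p) reaches 0.80 at p = 8.1% (8.2% with 66 per arm). Below a comparator rate of about 8%, even a true zipper rate of zero does not give 80% power.

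**Away from zero.** Exact power by full binomial enumeration of the same test, 67 per arm:

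| Rate in better arm | Rate in other arm for 80% power | Gap (points) |
|---|---|---|
| 0% | 8.1% | 8.1 |
| 1% | 11.8% | 10.8 |
| 2% | 14.2% | 12.2 |
| 5% | 20.5% | 15.5 |
| 10% | 28.7% | 18.7 |

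Read from the comparator side, rates of 10, 15, 20, 30 and 40% need a zipper rate of about 0.5, 2.3, 4.7, 10.9 and 18.3%.

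**Halving of risk.** Exact power is 10% for 5% versus 2.5%, 20% for 10% versus 5%, 72% for 40% versus 20%, and 80% for 45% versus 22.5%.

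**Small gaps.** Over comparator rates up to 50%, power is at most 15% for a 3-point gap and at most 43% for a 5-point gap.

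**Sensitivity of the floor to the assumptions.**

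| Method | Floor (points, from a zero-rate arm) |
|---|---|
| Pairwise exact chi-squared, two-sided 0.05 | 8.1 |
| Same, one-sided 0.05 or two-sided 0.10 | 6.3 |
| Zipper versus both comparators pooled (67 vs 133) | 7.6 |
| Three-group chi-squared, two arms at 0% | 6.3 |
| Normal approximation, pairwise | 10.9 |
| Fisher's exact test, pairwise | 11.5 |
| Normal approximation, Bonferroni 0.05/3 | 14.2 |

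**Inputs that would give about 200.** The pooled-variance formula is n per arm = [1.96·√(2p̄(1−p̄)) + 0.842·√(p₁(1−p₁)+p₂(1−p₂))]² / (p₁−p₂)². For 23% versus 6%, p̄ = 0.145, so n = (0.976 + 0.407)²/0.17² = 1.912/0.0289 = 66. The pairs 32% versus 12% and 40% versus 18% also give about 66. These are gaps of 17, 20 and 22 points.

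**Precision.** With a common rate p, the approximate 95% CI half-width for a pairwise difference is 1.96·√(2p(1−p)/67). This is 7.4 points at p = 5%, 10.2 at 10% and 13.5 at 20%.

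**The case against.** The strongest reply is that the descriptions of low and comparable risk were not written as planning inputs. One sits in the Risks section and concerns the harm of being randomised; the other justifies randomising at all. A power calculation uses a hypothesised effect, and section 1.1 hypothesises a reduction with the zipper. An equipoise statement beside a superiority hypothesis is normal. The endpoint is also open-ended and includes prolonged drainage, so the rate of any complication need not be small.

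Much of this stands. The words low and minimal carry no number, so the shortfall is conditional. A reader might infer that the calculation in section 5.1 is wrong, or that the trial certainly has less than 80% power. The documents do not support that, because a large assumed reduction from a sizeable comparator rate gives about 80%. What does not fall away is that section 5.1 names past incidence rates as its source, and every statement the protocol makes about past rates points to small differences. Nothing in the text supplies the large reduction that would be needed.

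A reader might also take 8 points as the difference this trial can detect. That would be wrong. It is a floor that holds only when one arm has a true rate of zero, and only under one assumed test. By the same exact test an 8-point gap has 61% power at 1% versus 9%, 38% at 5% versus 13%, 26% at 10% versus 18%, and 19% at 20% versus 28%.

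**Conclusion.** The point holds as a conflict between a stated power and the protocol's own description of the evidence, and it should be fixed. Under a pairwise uncorrected chi-squared test at two-sided 0.05 with 67 per arm, 80% power needs gaps of about 11 to 16 points when the better arm has 1 to 5%. In the best case, with a zero-rate arm, it needs about 8. The more lenient readings tried lower that best case only to about 6 points, again with at least one arm free of complications; Fisher's test or a multiplicity adjustment raises it. Dropout would also reduce power.

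The assumptions are mine where section 5.1 is silent, and the rates used are illustrative. The conclusion is that the 80% is unsupported and hard to square with rates described as low and minimally different. It is not that a stated calculation has been disproved, nor that 200 is the wrong number of patients.

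**What to change.** Keep 200 patients. In section 5.1, replace the unqualified 80% with the difference that 66 to 67 per arm can detect across a stated range of comparator rates, together with the expected 95% CI half-width at those rates. Retain 80% only for a named pair of rates, with their source, an alpha and a contrast that together deliver it.

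This changes protocol wording only; size and conduct are untouched. The cost is a less favourable power statement, unless the sponsor's actual inputs turn out to support 80%.

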5.2 Statistical Methods

Data on patient baseline characteristics, procedural characteristics, perioperative outcomes, functional outcomes, and costs will be collected. Single variable and multivariate statistical analysis will be performed to assess the aforementioned data points. Dichotomous data outcomes will be analyzed using odd ratios and chi-squared tests while continuous data points will be analyzed using Student t-tests. Each complication will be documented for every patient. The rates of complication will be analyzed individually for each technique, and risk ratios will be conducted between techniques to determine which technique has the lowest risk of developing a complication. Complications include infection, abscess formation, dehiscence, prolonged drainage, allergic reactions, among others. Cost effectiveness will be determined by the differences in quality metrics such as LOS, readmissions, cost of supplies, and differences in wound closure time between the different wound closure techniques. Each of these variables will be calculated based on the associated hospital costs and analyzed to determine the most cost effective wound closure technique.

CONFIDENTIAL

This material is the property of the NYU School of Medicine and Langone Medical Center. Do not disclose or use except as authorized in writing by the study sponsor

6 Safety and Adverse Events

6.1 Definitions

Unanticipated Problems Involving Risk to Subjects or Others

Any incident, experience, or outcome that meets all of the following criteria:

- Unexpected in nature, severity, or frequency (i.e. not described in study-related documents such as the IRB-approved protocol or consent form, the investigators brochure, etc)
- Related or possibly related to participation in the research (i.e. possibly related means there is a reasonable possibility that the incident experience, or outcome may have been caused by the procedures involved in the research)
- Suggests that the research places subjects or others at greater risk of harm (including physical, psychological, economic, or social harm).

Adverse Event

An **adverse event** (AE) is any symptom, sign, illness or experience that develops or worsens in severity during the course of the study. Intercurrent illnesses or injuries should be regarded as adverse events. Abnormal results of diagnostic procedures are considered to be adverse events if the abnormality:

- results in study withdrawal
- is associated with a serious adverse event
- is associated with clinical signs or symptoms
- leads to additional treatment or to further diagnostic tests
- is considered by the investigator to be of clinical significance

Serious Adverse Event

Adverse events are classified as serious or non-serious. A **serious adverse event** is any AE that is:

- fatal
- life-threatening
- requires or prolongs hospital stay
- results in persistent or significant disability or incapacity
- a congenital anomaly or birth defect
- an important medical event

CONFIDENTIAL

This material is the property of the NYU School of Medicine and Langone Medical Center. Do not disclose or use except as authorized in writing by the study sponsor

Important medical events are those that may not be immediately life threatening, but are clearly of major clinical significance. They may jeopardize the subject, and may require intervention to prevent one of the other serious outcomes noted above. For example, drug overdose or abuse, a seizure that did not result in in-patient hospitalization, or intensive treatment of bronchospasm in an emergency department would typically be considered serious.

All adverse events that do not meet any of the criteria for serious should be regarded as ***non-serious adverse events***.

Adverse Event Reporting Period

The study period during which adverse events must be reported is normally defined as the period from the initiation of any study procedures to the end of the study treatment follow-up. For this study, the study treatment follow-up is defined as 30 days following the last administration of study treatment.

Preexisting Condition

A preexisting condition is one that is present at the start of the study. A preexisting condition should be recorded as an adverse event if the frequency, intensity, or the character of the condition worsens during the study period.

General Physical Examination Findings

At screening, any clinically significant abnormality should be recorded as a preexisting condition. At the end of the study, any new clinically significant findings/abnormalities that meet the definition of an adverse event must also be recorded and documented as an adverse event.

Post-study Adverse Event

All unresolved adverse events should be followed by the investigator until the events are resolved, the subject is lost to follow-up, or the adverse event is otherwise explained. At the last scheduled visit, the investigator should instruct each subject to report any subsequent event(s) that the subject, or the subject's personal physician, believes might reasonably be related to participation in this study. The investigator should notify the study sponsor of any death or adverse event occurring at any time after a subject has discontinued or terminated study participation that may reasonably be related to this study. The sponsor should also be notified if the investigator should become aware of the development of cancer or of a congenital anomaly in a subsequently conceived offspring of a subject that has participated in this study.

Abnormal Laboratory Values

A clinical laboratory abnormality should be documented as an adverse event if any one of the following conditions is met:

- The laboratory abnormality is not otherwise refuted by a repeat test to confirm the abnormality
- The abnormality suggests a disease and/or organ toxicity

CONFIDENTIAL

This material is the property of the NYU School of Medicine and Langone Medical Center. Do not disclose or use except as authorized in writing by the study sponsor

- The abnormality is of a degree that requires active management; e.g. change of dose, discontinuation of the drug, more frequent follow-up assessments, further diagnostic investigation, etc.

Hospitalization, Prolonged Hospitalization or Surgery

Any adverse event that results in hospitalization or prolonged hospitalization should be documented and reported as a serious adverse event unless specifically instructed otherwise in this protocol. Any condition responsible for surgery should be documented as an adverse event if the condition meets the criteria for an adverse event.

Neither the condition, hospitalization, prolonged hospitalization, nor surgery are reported as an adverse event in the following circumstances:

- Hospitalization or prolonged hospitalization for diagnostic or elective surgical procedures for a preexisting condition. Surgery should **not** be reported as an outcome of an adverse event if the purpose of the surgery was elective or diagnostic and the outcome was uneventful.
- Hospitalization or prolonged hospitalization required to allow efficacy measurement for the study.
- Hospitalization or prolonged hospitalization for therapy of the target disease of the study, unless it is a worsening or increase in frequency of hospital admissions as judged by the clinical investigator.

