A single-center, phase IV, randomized, prospective study investigating the efficacy of various wound closure devices in reducing postoperative wound complications

Regulatory Sponsor: **[name]**

Co-Investigators: [name]
[name]

NYULMC Orthopaedic Surgery
Hospital of Joint Diseases
[name]
[name]

Study Product: Zipper wound closure device, Monocryl + Dermabond,
Polyester mesh + Dermabond

Protocol Number: s16-02020

NCT Number: NCT03134209

Version: 1/10/17

CONFIDENTIAL

This material is the property of the NYU School of Medicine and Langone Medical Center. Do not disclose or use except as authorized in writing by the study sponsor

Initial version: 12/15/16

List of Abbreviations

TJA- Total joint arthroplasty

CONFIDENTIAL

This material is the property of the NYU School of Medicine and Langone Medical Center. Do not disclose or use except as
authorized in writing by the study sponsor

Study Summary

Title	A single-center, phase IV, randomized, prospective study investigating the efficacy of various wound closure devices in reducing postoperative wound complications
Short Title	Assessing various wound closure techniques; RCT
Protocol Number	i16-02020
Phase	4
Methodology	Randomized, control
Study Duration	7 months
Study Center(s)	Single-center
Objectives	To determine the efficacy of the experimental wound closure device in regards to reducing wound complications and costs
Number of Subjects	200 subjects
Diagnosis and Main Inclusion Criteria	Patients who are undergoing joint arthroplasty
Study Product, Dose, Route, Regimen	Zipper surgical skin closure device applied to the most superficial layer of skin following a joint arthroplasty
Duration of administration	Applied one-time to close the wound following joint arthroplasty. This device will be applied for up to 2-3 weeks
Reference therapy	Experimental treatment will be compared to two groups: 1) Monocryl + Dermabond 2) Polyester mesh + Dermabond
Statistical Methodology	Odd ratios will be used to determine which wound closure device is at higher risk of developing a wound complication

CONFIDENTIAL

This material is the property of the NYU School of Medicine and Langone Medical Center. Do not disclose or use except as authorized in writing by the study sponsor

Introduction

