2.1 General Design

A single-center, phase IV, randomized, prospective study. Patients will be expected to participate for about 4 months. Please refer to section 4 for a summary description of the sequence and duration of all trial periods including follow-up.

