3.4 Blinding of Study Product

Given the nature of the application of the wound closure device, which will be visible to the surgeon at the time of application and the patient postoperatively, the study will not be blinded to either the surgeon or the patient. Prior to discharge, a blinded plastic surgeon will be asked to assess the wound based on comessis and overall quality of wound healing.

4 Study Procedures

Patients who are eligible for the study will be notified on a preoperative visit via a tool on the electronic medical record system (Epic).

At this time, surgeon research assistant will ask the patient if they would like to be involved in the study. If consent to participate in the study is given, the surgeon will go ahead with the randomization process, which will dictate what type of wound closure device will be used at the time of the surgery. All of the wound devices are currently being used at the institution. The study will follow normal standard of care for the application of these devices. The only different will be the randomization process that will take place prior to the surgery. Data will be collected regarding the primary outcomes at the time of discharge as well as at their normally scheduled postoperative visits. Patients will be followed up to their 3rd postoperative visit. Prior to discharge, a plastic surgeon, who will be blinded to the type of wound closure technique that the patient received, will assess the wound for the quality of wound healing. At their postoperative visits, the physician will document whether a complication had occurred. Patients will also be given patient-reported outcome questionnaires, including VAS scores and HWES, that will measure the level of satisfaction of their wound healing at the time of these visits.

The following table shows the visits and procedures/ observational data collection that will occur during the study:

Activity	Pre-operative assessment	Date of surgery	Prior to discharge	Postop visit #1	Postop visit #2	Postop visit #3
Study team procedures						
Consent	X					
Medical History	X			X	X	X
Physical Exam	X		X	X	X	X
Height	X			X	X	X
Weight	X			X	X	X
Vitals signs	X		X	X	X	X
Record of			X	X	X	X

CONFIDENTIAL

This material is the property of the NYU School of Medicine and Langone Medical Center. Do not disclose or use except as authorized in writing by the study sponsor

complications						

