6.2 Recording of Adverse Events

At each contact with the subject, the investigator must seek information on adverse events by specific questioning and, as appropriate, by examination. Information on all adverse events should be recorded immediately in the source document, and also in the appropriate adverse event module of the case report form (CRF). All clearly related signs, symptoms, and abnormal diagnostic procedures results should be recorded in the source document, though should be grouped under one diagnosis.

All adverse events occurring during the study period must be recorded. The clinical course of each event should be followed until resolution, stabilization, or until it has been determined that the study treatment or participation is not the cause. Serious adverse events that are still ongoing at the end of the study period must be followed up to determine the final outcome. Any serious adverse event that occurs after the study period and is considered to be possibly related to the study treatment or study participation should be recorded and reported immediately.

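### The adverse event reporting period closes 30 days after last administration, before follow-up ends, and the protocol's other AE rules conflict with that cut-off

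*Combined protocol and SAP*

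**What the plan says.** Section 6.1, under Adverse Event Reporting Period, says that AEs must be reported over "the period from the initiation of any study procedures to the end of the study treatment follow-up". It then fixes the end point for this trial: "the study treatment follow-up is defined as 30 days following the last administration of study treatment". Section 6.2 makes AE recording mandatory within that study period. For later events it adds one rule: "Any serious adverse event that occurs after the study period and is considered to be possibly related" to treatment or participation is to be recorded and reported at once.

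Follow-up is described differently elsewhere. Section 2.1 says "Patients will be expected to participate for about 4 months". Section 4 says "Patients will be followed up to their 3rd postoperative visit" and "At their postoperative visits, the physician will document whether a complication had occurred". No day or week is given for the third visit.

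The Study Summary describes administration in two ways in the same row, Duration of administration: "Applied one-time to close the wound following joint arthroplasty", followed by "This device will be applied for up to 2-3 weeks". No wear time is given for the two comparator closures.

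**The concern.** Two clocks run on the same patients. Infection, dehiscence, prolonged drainage and allergic reaction are primary complications, recorded to the third visit. They also meet the AE definition. On a strict reading of Sections 6.1 and 6.2, one of these events seen late in follow-up counts for the endpoint but need not be entered as an AE unless it is serious and possibly related. AEs that are not wound complications have no second route into the data.

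At stake are the completeness of the AE record after day 30 and the biweekly review in Section 8.1, which is meant to look at how many AEs there are and how severe. Staff who follow the 30-day sentence and staff who follow the instruction to ask at each contact would record different things. The rule for late serious events also turns on a relatedness judgement, and Section 3.4 leaves the surgeon unblinded. A late serious event judged unrelated therefore also lacks a clear rule.

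**Working it through.** The 30 days is a definition, so there is no planned figure to reproduce. The check is calendar arithmetic, then a comparison of the rules.

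**Inputs**
- Participation: about 4 months (Section 2.1), taken as 4 × 365.25/12 = 121.75 days.
- End of the AE period: 30 days after last administration (Section 6.1).
- Start of participation: consent at a preoperative visit (Section 4). The interval L from consent to surgery is not stated; 0 to 60 days is my assumption.
- Third postoperative visit: not dated; assumed to fall at the end of participation.
- Administration: first read as one-time application on the day of surgery.

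**Formulas.** Postoperative follow-up F = 121.75 − L. Days after the window U = F − 30. Share = U/F.

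| L (assumed) | F | U | U/F |
|---|---|---|---|
| 0 | 121.75 | 91.75 | 75% |
| 14 | 107.75 | 77.75 | 72% |
| 30 | 91.75 | 61.75 | 67% |
| 45 | 76.75 | 46.75 | 61% |
| 60 | 61.75 | 31.75 | 51% |

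So about 92 to 32 postoperative days lie after the window. With visit 3 at the end of participation, the gap closes only if L reaches 121.75 − 30 = 91.75 days. An earlier third visit would shorten the gap to that visit day for day.

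**If zipper wear counted as administration.** With 14 to 21 days of wear, the zipper window would end on day 14 + 30 = 44 to 21 + 30 = 51. The days left over would be 121.75 − 44 = 77.75 to 121.75 − 51 = 70.75 at L = 0, and 61.75 − 44 = 17.75 to 61.75 − 51 = 10.75 at L = 60. The gap shrinks but remains. The difference between arms would be zipper wear minus comparator wear. The second term is not in the documents, so the difference cannot be calculated.

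**Rules for an AE that starts between day 31 and the third visit**
- Section 6.1, reporting period: outside.
- Section 6.2, mandatory recording: outside, unless serious and possibly related.
- Section 6.1, AE definition: inside, because it covers anything arising or worsening while the study runs.
- Section 6.2, questioning at each contact with all AE information entered in the source and the CRF: inside, with no day limit.
- Section 6.1, new clinically significant findings at the end of the study: recorded as AEs, but an event already resolved by then is not clearly covered.
- Section 6.1, notification of post-study events: not applicable, because the patient has neither discontinued nor finished participation.
- Section 4, complication recording: a wound complication is captured in every arm.

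Two rules exclude such an event and two include it. The end-of-study rule does not settle the case of an AE that resolves before the last visit.

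**The case against.** The strongest reply is that the protocol does not stop collecting harms at day 30. AEs are sought at every contact, and the postoperative visits are contacts. New significant findings at the end of the study must be recorded as AEs, serious or not. Related AEs after participation ends go to the sponsor, again serious or not. The wound harms that matter most for a closure device are recorded to the third visit in all arms. All of this stands. It rules out several stronger readings:

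- A reader might infer that every later non-serious harm falls outside safety reporting. The provisions above reach past day 30, so the text is contradictory and does not set a clean stop.
- A reader might infer a biased comparison between arms. Section 5.2 plans no between-arm AE analysis, and the planned comparison uses complications, which follow the visit schedule.
- A reader might infer that the zipper arm has a longer AE window. That requires wear time to count as administration. Under the one-time wording the window ends on postoperative day 30 in every arm.
- A reader might divide 30 days by 4 months and conclude that only a quarter of participation is covered. The period starts with the first study procedure, so coverage is (L + 30)/121.75: 25% at L = 0, but 49% at L = 30 and 74% at L = 60.

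The reply does not remove the conflict. The instruction to ask at each contact contradicts the 30-day period without overriding it, and the post-study rule does not apply to patients still in follow-up.

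**Conclusion.** The point holds as an internal contradiction with a limited effect. Between postoperative day 31 and the third visit, the protocol gives no consistent rule for an AE that is non-serious, or serious but judged unrelated, and that resolves before the last visit. The stretch concerned is about 92 to 32 days, at least half of postoperative follow-up across the assumed range. This rests on one-time application on the day of surgery, a lead time of 0 to 60 days, and a third visit at the end of participation; none of the three is fixed by the documents. The meaning of last administration is a separate ambiguity. It could make the window differ by arm, by an amount that cannot be stated. The primary complication comparison is not affected.

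**What to change.** Replace the 30-day sentence in Section 6.1 with one rule, for example: AEs are recorded in all arms from the start of study procedures to the third postoperative visit, which takes place a stated number of days after surgery. The sponsor should supply that number and the visit window, make them fit the participation period in Section 2.1, and use the same visit as the end date for complication recording in Section 4. An end date counted from surgery no longer depends on what last administration means. The two descriptions in the Study Summary should still be reconciled, and the AE definition in Section 6.1 and the recording rules in Section 6.2 aligned with the new period.

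The cost is a short protocol edit and a few more AE entries at visits already scheduled with history, examination and complication recording. No visit or procedure is added.
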